14.9 Degree of Severity of Adverse Events

- **Mild:** Awareness of the event, but easily tolerated by subject
- **Moderate:** Discomfort enough to cause interference with usual activity
- **Severe:** Inability to carry out usual activity

14.10 Device Failures, Malfunctions and Near Incidents

Device failures or malfunctions will be reported to Sponsor by the clinical sites. If the failure or malfunction results in negative clinical sequelae, the event shall be reported to the Sponsor within two (2) working days after the Investigator becomes aware of the device-related adverse event and reported to the IRB/EC (if required) within the IRB/EC required timeframe. The malfunctioning device involved in the incident should be returned to the Sponsor for evaluation.

14.11 Independent Review of Retroperitoneal Ultrasound (renal and bladder)

An independent reviewer will review all baseline, 2 week (if applicable) and 6 week retroperitoneal ultrasounds to assess for any unreported device-related serious complications defined as:

- Device perforation of the rectum or GI tract

- Device related formation of fistula between the rectum and urethra
- Permanent damage to the bladder, trigone or ureteral orifices requiring intervention

If any of the above are noted, a request will be sent to the site to report such event. Copies of the retroperitoneal ultrasound will be available for the CEC if they deem necessary.

15 Training

The Sponsor will be responsible for training appropriate clinical site study personnel. All physicians proctored by the Sponsor, as well as other trained physicians, must have completed the commercial training program. To ensure proper procedural technique, uniform data collection and protocol compliance, the Sponsor will present a formal training session to personnel at each study site. At this training session the Sponsor will review the study protocol, techniques for the identification of eligible subjects, instructions on data collection, schedules for follow-up assessments, and regulatory requirements.

16 Data Management

16.1 Subject Identification

Subjects who successfully pass the screening tests and wish to participate in the study will be assigned a unique identification code (ID) using the format “XXX-YYY” where:

XXX = Institution Number, assigned by the Sponsor to each study site

YYY = Enrollment Number, assigned by the institution as each subject is enrolled in the study

In addition to the ID, each subject’s initials will be used as an identifier included on documentation submitted to the Sponsor.

16.2 Central Database

All study documentation will be collected and compiled in a central database. Appropriate quality control measures will be established to ensure accurate and complete transfer of information from the study documentation to the central database.

17 Study Responsibilities and Management

The proposed study will be performed in accordance with all requirements set forth in the U.S. regulations, 21 Code of Federal Regulations (CFR) Parts 812, 50, 54, and 56, the World Medical Association Declaration of Helsinki, and any other applicable local laws, regulations, or guidelines in the applicable countries where the study may occur.

17.1 Investigator Responsibilities

Each investigator is responsible for ensuring the investigation is conducted according to all signed agreements, the study protocol, EC/IRB requirements, and applicable laws and regulations. Also,

Investigators may not begin enrollment until Sponsor or its designee receives and approves (when necessary) the following documents:

- Signed Investigator Agreement,
- Financial disclosure forms for all participating investigators,
- EC/IRB roster (or IRB registration no. from the Office of Human Research Protection),
- EC/IRB protocol and ICF approvals,
- Investigators' current curricula vitae (CV), and
- Signed Site Delegation Log.

It is acceptable for Investigators to delegate one or more of the above functions to an associate or Co- or Sub-Investigator, or a trained Study Coordinator; however, the Investigator remains responsible for the proper conduct of the clinical investigation, including obtaining and documenting proper study informed consent, collecting all required data, submitting accurate and complete CRFs, etc.

At each study site, appropriate procedures must be followed to maintain subject confidentiality according to appropriate local regulations (e.g., Health Insurance Portability and Accountability Act (HIPAA) in the U.S.). Each site may have its own internal procedures or requirements for use and release of subject medical information in research studies. Each Investigator is responsible for obtaining appropriate approvals, consents, or releases of medical information as dictated by their relevant subject privacy laws.

The study is not transferable to other sites attended by the Investigator unless prior approval is obtained from the appropriate EC/IRB and the Sponsor.

17.2 Subject Enrollment Process

All study candidates, after pre-procedure screening, must appropriately consent to participate in the study, as administrated by qualified study site personnel using an IRB and Sponsor-approved ICF prior to beginning any aspect of the study procedure or tests that are not standard of care for the site. Investigational sites will be required to document the consent process within each enrolled subjects medical record. Administering the questionnaires can be done prior to signing the ICF. Only subjects who meet the inclusion/exclusion criteria, who signed the study informed consent and completed device insertion will be considered enrolled in the study.

Timely communication by each site is critical to avoid over enrolling when the enrollment is close to the end of each phase. When enrollment is close to the end of each phase, the following procedures may be implemented:

- Before the subject signs the study ICF, the Study Coordinator must confirm the availability of an enrollment slot. A phone call to the Sponsor is the preferred method.
- Immediately after the procedure, the Study Coordinator must inform (phone call or fax or e-mail) the Sponsor to confirm the subject's eligibility and the completion of the procedure. A phone call to the Sponsor is the preferred method.

17.3 Ethics Committee (EC) / Institutional Review Board (IRB)

Investigators must submit the study protocol to their respective EC and/or IRB and obtain the EC's/IRB's written approval before being allowed to conduct and participate in the study. Each Investigator is responsible for fulfilling any conditions of approval imposed by their respective EC/IRB, such as regular reporting, study timing, etc. Investigators will provide the Sponsor or its designee with copies of such approvals and reports.

17.4 Informed Consent Form (ICF)

The Sponsor will provide a template ICF to each study site for EC/IRB submission. The template may be modified to suit the requirements of the individual study site but the Sponsor must pre-approve all changes to the ICF prior to initial submission to the EC/IRB.

Each Investigator or assigned designee must administer this approved ICF to each prospective study subject, and obtain the subject's signature or a legally-approved designee's signature along with the date of consent prior to enrollment in the study. The ICF must be obtained in accordance with the applicable guidelines on 21 CFR 50, 52 and 56, the Declaration of Helsinki, ISO 14155 or local regulations and laws, whichever represents the greater protection of the individual. Subjects must be informed about their right to withdraw from the study at any time and for any reason without sanction, penalty, or loss of benefits to which the subject is otherwise entitled and also be informed that withdrawal from the study will not jeopardize their future medical care. A copy of their signed ICF must be given to each subject enrolled in the study. The institutional standard subject consent form does not replace the Rezūm XL study ICF.

17.5 Case Report Forms (CRFs)

The Sponsor will provide standardized CRFs for each individual subject. The standardized CRFs will be electronic (EDC, 21 CFR Part 11 compliant), and will be used to record study data, and are an integral part of the study and subsequent reports.

The electronic CRFs for individual subjects will be provided by the Sponsor via a web portal. After the data have been monitored and submitted, corrections will be initiated via a data query or DCF to be completed by study site personnel. This DCF also will be done electronically via the web portal. Electronic CRFs must be approved and signed by the Investigator in the appropriate spaces provided using his/her electronic signature.

17.6 Records

Each Investigator must maintain the following accurate, complete, and current records relating to the conduct of the study investigation. The final responsibility for maintaining such records remains with the Investigator. These records include, but are not limited to:

- All signed agreements;
- IRB/EC approval letter(s);
- Signed ICF;
- Records of AEs, including supporting documents;

- Records of protocol deviations, including supporting documents
- Records showing receipt, use and disposition of all devices, including:
 - Date, quantity, model and lot numbers of devices received,
 - Name of person(s) who received, used or disposed of each device,
 - The number of devices returned to the Sponsor and the reason(s) for return;
- All correspondence related to the study;
- Records of each subject’s case history, including study-required CRFs, signed ICF, all relevant observations of AEs, the condition of each subject upon entering and during the course of the investigation, relevant medical history, the results of all diagnostic testing, etc.;
- Study personnel visit log;
- Signature authorization and delegation log; and,
- Any other records that applicable regulation requires to be maintained.

17.7 Reports

Table 17-1 lists those reports that are the investigator's responsibility to deliver to the Sponsor. Each study investigator must follow the EC/IRB reporting requirements for their respective site. If applicable regulations or EC/IRB requirements mandate stricter reporting requirements than those listed, the stricter requirements must be followed.

TABLE 17-1: REPORTS REQUIRED FROM INVESTIGATORS TO SPONSOR

Type of Report	Prepared by PI for	Notification Time Frame
UADE	Sponsor, EC/IRB	Within 10 working days of knowledge
Death	Sponsor, EC/IRB	Written reports (e.g., via e-mail) within 48 hours
SAE	Sponsor EC/IRB, if required	Within 10 working days of knowledge Per IRB requirement
Device malfunction with clinical sequelae	Sponsor EC/IRB, if required	Within 48 hours via written communication. Return the device to sponsor within 48 hours.
Serious protocol deviations (e.g., ICF not obtained, to protect the life or physical well-being of a subject in an emergency)	Sponsor EC/IRB, if required	Within 5 working days of knowledge Per IRB requirement
Withdrawal of EC/IRB approval	Sponsor	Within 5 working days of knowledge
Annual progress report	Sponsor, EC/IRB	Annually
Final report	Sponsor, EC/IRB	Within 3 months of study completion or termination
Note: Each IRB/EC may require more stringent reporting requirements than those listed in this table.		

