9.3.3 Safety Monitoring Early Stopping Rule

An early stopping rule is instituted in the study to monitor the rate of steam-related injury.

This early stopping rule is intended to provide a higher degree of sensitivity to steam-related injury and earlier time-frame than is provided by the primary safety endpoint composite which includes a wider spectrum of adverse events and a longer time period of 6-months post-procedure.

If 2 patients experience a post-procedure CEC-determined device-related steam-related injury requiring intervention within the first 20 subjects treated with Rezūm, the early 6 week post procedure stopping rule is triggered. A threshold of 2 patients with an event out of the first 20 subjects is an observed event rate of 10%.

For the study stopping rule “Intervention” is defined as any surgical procedure or hospitalization performed to remedy or correct a potential permanent damage to the bladder, trigone or ureteral orifices, perforation of the rectum or GI tract, or formation of fistula between the rectum and urethra or bladder.

Irrigation of clot retention or necrotic tissue obstruction is allowed, if medically necessary, and should be reported as an adverse event but will not be counted toward the stopping rule.

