14.5 Definition of Serious Adverse Event(s)

An AE is considered to be an SAE if it resulted, or could result in, if not mitigated:

- Death;
- A life-threatening situation;
- Requires the subject to be hospitalized or prolongs an existing hospitalization;
- Persistent or significant disability/incapacity; or,
- Is considered an important medical event.

Important medical events that may not meet one of the above definitions could be considered SAEs if they jeopardize the health of the subject or require surgical intervention to prevent one of the outcomes listed above. An SAE may or may not be related to the study procedure.

Classification of an AE to an SAE will be decided by the CEC.

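### A stopping-rule injury from a correctly working device has a 10-working-day limit for reporting to the sponsor, against 48 hours for a death or a malfunction with sequelae; a 48-hour row would be a cheap improvement

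*Combined protocol and SAP*

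**What the plan says.** **Reporting limits (17.7, Table 17-1).**
- SAE and UADE, to the sponsor: "Within 10 working days of knowledge".
- Death: "Written reports (e.g., via e-mail) within 48 hours".
- Device malfunction with clinical sequelae: "Within 48 hours via written communication". Section 14.10 words the same duty slightly differently: "the event shall be reported to the Sponsor within two (2) working days after the Investigator becomes aware of the device-related adverse event".
- Serious protocol deviation, and withdrawal of EC/IRB approval: 5 working days.
- The text above the table adds: "If applicable regulations or EC/IRB requirements mandate stricter reporting requirements than those listed, the stricter requirements must be followed".

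**Stopping rule (9.3.3).** The rule is triggered by 2 CEC-determined, device-related steam injuries requiring intervention among the first 20 men treated. It is "intended to provide a higher degree of sensitivity to steam-related injury and earlier time-frame than is provided by the primary safety endpoint composite". Intervention means "any surgical procedure or hospitalization performed to remedy or correct a potential permanent damage to the bladder, trigone or ureteral orifices", and likewise for rectal or GI perforation and for fistula from the rectum to the urethra or bladder. A malfunction is not required. The section gives no reporting deadline.

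**Seriousness (14.5).** "An AE is considered to be an SAE if it resulted, or could result in, if not mitigated": the list that follows includes hospitalization, disability and important medical events, and an event needing surgery to prevent such outcomes can qualify. The CEC decides the classification.

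**UADE (14.6).** Notice to the sponsor is to be prompt, but no number of days is given. The sponsor must suspend the study if it finds that a UADE poses an unreasonable risk.

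**The concern.** The hazard that 9.3.3 was written to catch can occur with a device that works as designed. Section 7.1 itself attributes possible perforation to errors in placement. Such an injury misses the 48-hour malfunction row and falls into a two-week row. A missing consent form, at 5 working days, is due at the sponsor sooner than a rectal perforation.

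The rule counts events across up to 11 sites, so no single site sees the total. The sponsor and CEC can act on an injury only once they know of it. What is at stake is the number of men treated between the site's knowledge and the sponsor's. No hypothesis, endpoint or sample size is affected.

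**Working it through.** **1. Which row applies.** A 9.3.3 event needs surgery or hospitalization to count. Hospitalization is an SAE criterion in 14.5, and surgery to avert a listed outcome can make an event an important medical event. Perforation and rectal fistula are on the anticipated list in 14.4, so SAE is the likelier route. UADE remains possible on degree of incidence, because 7.1 reports no perforation to date. Both routes carry 10 working days in Table 17-1. Section 14.10 covers only failures and malfunctions.

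**2. The plan's own figure.** 2/20 = 10%, as 9.3.3 states. This is the observed rate that triggers the rule, not an expected rate.

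**3. Men treated during the lag.** Inputs: 88 men and 6 months' enrolment (9.2). Assumptions: uniform accrual, full window used, 10 working days = 2 weeks. The planned rate is 88/26 = 3.385 men per week. The 12- and 24-month rows are illustrative.

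| Enrolment | Men/week | 10 working days | 48 hours (2/7 week) | Two working days over a weekend (4/7 week) | Excess |
|---|---|---|---|---|---|
| 6 months (26 weeks) | 3.385 | 6.77 | 0.97 | 1.93 | 4.84 to 5.80 |
| 12 months (52 weeks) | 1.692 | 3.38 | 0.48 | 0.97 | 2.42 to 2.90 |
| 24 months (104 weeks) | 0.846 | 1.69 | 0.24 | 0.48 | 1.21 to 1.45 |

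**4. Injuries among the excess men, at the planned pace.** The documents give no rate for these injuries in large prostates, so every p below is assumed. X ~ Bin(20, p). Given a trigger, the expected number is excess × p. Unconditionally it is excess × p × P(X ≥ 2).

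| p | P(X ≥ 2) | Given a trigger | Unconditional |
|---|---|---|---|
| 10% | 0.608 | 0.48 to 0.58 | 0.29 to 0.35 |
| 5% | 0.264 | 0.24 to 0.29 | 0.064 to 0.077 |
| 2% | 0.060 | 0.097 to 0.116 | 0.0058 to 0.0070 |
| 1% | 0.017 | 0.048 to 0.058 | 0.0008 to 0.0010 |

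**5. A guide from section 8.** The pilot (65 men) and the Rezūm II treatment arm (136) describe no injury of the 9.3.3 kind. With 0/201, the one-sided 95% upper bound is 1 − 0.05^(1/201) = 0.0148, about 1.5%. At 1.5%, P(X ≥ 2) is about 0.036, and the unconditional figure is 4.84 × 0.015 × 0.036 = 0.0026 to 5.80 × 0.015 × 0.036 = 0.0031. These were mostly smaller prostates, so this does not bound the rate here.

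**6. What faster reporting does not reach.** The 20th man is treated at 20/3.385 = 5.9 weeks and completes 6 weeks at week 11.9. By then 3.385 × 11.9 = 40.3 men have been treated. Section 19.1 sets no deadline for CEC adjudication.

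**The case against.** The table is coherent and applies as written. The malfunction row has a purpose of its own, since it also requires return of the device within 48 hours, so it is no evidence that steam injury was overlooked.

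Sponsor and CEC knowledge also does not depend on Table 17-1 alone:
- Every man has a recorded cystoscopy immediately after treatment, and visible injury must be reported as an AE (10.4.2). The videos go to the sponsor and CEC (11.4; Table 10-2, footnote 2).
- Retroperitoneal ultrasounds at 6 weeks, and at 2 weeks where done, are independently read for unreported complications (14.11).
- UADE notice is to be prompt, and stricter regulations or EC/IRB rules override the table.

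Signatory agreements and the monitoring plan are not in the document, and the operative limit may be shorter.

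The benefit is also small at injury rates near prior experience. The rule needs a CEC determination after the report, and usually only the report that completes the pair delays the trigger.

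Most of this stands. It shows that the figures in the working are ceilings and that the gain is modest. It does not close the gap: the video and ultrasound channels have no stated deadline, the UADE wording has no number of days and may not apply, and the override operates only where a stricter rule exists.

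A reader might infer that sites will in fact wait two weeks, or that the sponsor will otherwise be unaware of the injury. The documents support neither; they set only an outer limit.

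**Conclusion.** The gap is real and narrow. For a 9.3.3 injury from a correctly working device, the protocol's only numeric limit for reporting to the sponsor is 10 working days, unless the man dies. That suits poorly a rule meant to give earlier warning than the 6-month composite. It is a safety improvement worth making, not the correction of an error.

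The ceiling is about 5 to 6 more men treated during the lag at planned accrual, or about 1 to 3 over 12 to 24 months. Early accrual is likely to be slower than uniform, so the lower figures may be closer for the first 20 men. Expected injuries avoided are about 0.001 to 0.007 at assumed rates of 1% to 2%, and about 0.3 only near 10%. All of this assumes that the whole window is used and that enrolment halts promptly once the report arrives.

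Two stronger readings are tempting. One is that the table contradicts 9.3.3 or makes the stopping rule unworkable; it does not, since the rule still operates and no test or result changes. The other is to treat 10% as the likely injury rate; 9.3.3 gives it only as the observed-rate threshold.

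**What to change.** Add one row to Table 17-1. It should cover any suspected device-related injury of the bladder, trigone or ureteral orifices, any rectal or GI perforation, and any fistula from the rectum to the urethra or bladder, where surgery or hospitalization has followed or is planned. The site reports it to the sponsor within 48 hours of knowledge, without waiting for the CEC to classify it. Add one sentence that the sponsor forwards it at once to the existing CEC.

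Keep 10 working days for other SAEs. Do not extend the row to Grade 2 hydronephrosis, which 9.3.3 does not count, or to blanching or erythema without intervention, which would enlarge the reporting load without serving the rule.

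The cost is faster reporting of a few events. No staff or procedures are added, because sites already have 48-hour written reporting for deaths and malfunctions. The row shortens only the first step: it does not set a CEC turnaround time or help with injuries that emerge late.

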17.8 Sponsor Responsibilities

NxThera, a Boston Scientific Company, is the Sponsor of this study. The Sponsors responsibilities in the study include:

- Selecting the Principal Investigator(s), all clinical investigators and study sites, and other consultants (e.g., monitors) who participate in the study.
- Provide study protocol, device, and GCP training to participating study sites, in quantities sufficient to support study activities, per agreements executed with the study sites.
- Select all qualified clinical Investigators and study sites and other consultants (e.g., the study monitors) who participate in the study.
- Provide financial support to each study site.
- Follow/promote all regulatory standards per appropriate regulations for study sites, core laboratories, and other participants, and ensure compliance by periodically monitoring sites.
- Ensure completion of site monitoring of clinical data at each clinical study site.
- Retain ownership of all clinical data generated in this study, and control the use of the data for appropriate purposes only.
- Review and approve publication of study results in the literature.

17.8.1 Confidentiality

All information and data sent to the Sponsor concerning subjects or their participation in this study will be considered confidential according to HIPAA regulations. Data used in the analysis and reporting of this evaluation will be used in a manner without identifiable reference to the subject. Investigators will consent to visits by Sponsor's staff and its authorized representatives, as well as by the U.S. FDA or any other local governmental body, to review the study subjects' medical records, including any test or laboratory data that might have been recorded on diagnostic test media (e.g., cystograms).

